### 6.1. Handling of Dropouts or Missing Data

Rules for handling dropouts or missing data are listed by type of analysis alphabetically. Unless otherwise specified, observed data will be used and missing data will not be imputed or carried forward.

#### General rules for imputing dates related to AEs or concomitant therapy:

- Onset date of an AE or start date of a concomitant therapy:
  - If only the day is missing, the date will be set to:
    - First day of the month that the event occurred, if the onset yyyy-mm is after the yyyy-mm of first study treatment.
    - The day of the first study treatment, if the onset yyyy-mm is the same as yyyy-mm of first study treatment.

- If both the day and month are missing, the complete date will be set to:
  - January 1 of the year of onset, if the onset year is after the year of the first study treatment.
  - The date of the first dose, if the onset year is the same as the year of the first study treatment.
- Resolution date of an AE or end date of a concomitant therapy:
  - If only the day is missing, the date will be set to the last day of the month of the occurrence, or to the date of death of the patient died in the same month.
  - If both the day and month are missing, the date will be set to December 31 of the year of occurrence, or to the date of death of the patient died in the same year.

If a date is completely missing, then the AE will be considered treatment emergent. In case of additional therapies, the therapy will be considered concomitant.

**General rule for imputing other dates:** If a date variable is needed for an analysis, use the following general rule to impute incomplete date:

- If the day of a date is missing, but not the month or year, then assign Day 1 of the month to the day.
- If the month of a date is missing, but not the day or the year, then assign January to the month.

After imputation, the imputed date should be logically consistent with other relevant date variable(s).

**Safety analysis:** The following rule for missing data processing will apply for safety analysis:

- Missing classifications concerning study medication relationship will be considered as related to study medication.
- If the AE onset date is missing or partial, the date will be compared as far as possible with the date of first dose of study medication when determining whether or not the AE is present at baseline. In this case, the AE will be assumed to be treatment emergent, unless there is clear evidence (through comparison of partial dates) to suggest that the AE started prior to the first dose of study medication.

**Time-to-event analysis:** All censored data will be accounted for using appropriate statistical methods.

## 6.2. Patient Disposition

All patient discontinuation data will be listed, including the extent of the patient participation in the study. If known, a reason for their discontinuation from treatment and from study will be listed and summarized. All patients entered in the study will be included in the summary and listing.

All significant protocol violations will be listed by pre-determined categories (eg, inclusion/exclusion criteria, errors/missing data in the informed consent/assent process, noncompliance with protocol procedures, errors and missing data in drug dosage/intervention, errors in recording DLTs, use of excluded treatments, patients continuing after meeting withdrawal criteria, or other violations as recorded on electronic case report form (eCRF) or monitoring reports).

### 6.3. Patient Characteristics

The following patient demographic and other baseline characteristics will be summarized:

- patient demographics: age (years) and age group (<12 vs.  $\geq 12$ ), gender, race, ethnicity, weight (kg), height (cm), body surface area (BSA) (m^2) and Performance Level (Karnofsky  $\geq 50\%$  for patients  $> 16$  years of age and Lansky  $\geq 50\%$  for patients  $\leq 16$  years of age, see protocol for details)
- baseline disease characteristics: initial pathological diagnosis type and subtype, disease stage at initial diagnosis only, current disease stage and duration of disease (months) at study entry
- prior cancer therapies

Patient listings of demographic data and baseline characteristics will be provided. Patient listings of prior cancer therapies (surgery, radiotherapy, and systemic therapy) will be provided.

### 6.4. Concomitant Therapy

The following concomitant medications will be summarized and listed for the safety population:

- Anticoagulation: Use of therapeutic anticoagulation with heparin, low-molecular weight heparin, or Coumadin should be avoided.
- Anti-platelet agents: Use of aspirin, ibuprofen or other non-steroidal anti-inflammatory drugs or anti-platelet agents for chronic use is not allowed while on study therapy.
- Anti-hypertensives: Patients who develop hypertension while on study therapy may be treated with anti-hypertensive agents and may remain on therapy as long as hypertension is well controlled on medication.

The use of belimumab (a monoclonal antibody for systemic lupus erythematosus) and bisphosphonate derivatives are prohibited while the patient is on study therapy.

### 6.5. Efficacy Analyses

#### 6.5.1. Efficacy Analysis Variables

Definition of efficacy analysis variables are listed below:

- **Objective response rate (ORR)** is defined as the proportion of treated patients achieving a best overall response of partial response (PR) or complete response (CR) per Response Evaluation Criteria in Solid Tumors Version 1.1(RECIST v.1.1). Patients who do not have any postbaseline tumor response assessments for any reason are considered nonresponders and are included in the denominator when calculating the response rate.
- **Disease control rate (DCR)** is defined as the proportion of treated patients achieving a best overall response of CR, PR, or stable disease (SD) per RECIST v.1.1. Patients who do not have any postbaseline tumor response assessments for any reason are considered non-responders and are included in the denominator when calculating the response rate.
- **Duration of response (DOR)** is defined from the date of first documented CR or PR (responder) to the date of objective progression or the date of death due to any cause, whichever is earlier. If a responder is not known to have died or have objective progression, then the patient will be censored at the date of last evaluable tumor assessment.
- **Progression-free survival (PFS)** is defined as the time from the date of randomization until the date of radiographic documentation of progression (as defined by RECIST v. 1.1) based on investigator assessment or the date of death due to any cause, whichever is earlier. The censoring is taken in the following order:
  - If a patient does not have a baseline disease assessment, then the PFS time will be censored at the randomization date, regardless of whether or not objective progressive disease (PD) or death has been observed for the patient.
  - If a patient is not known to have died or have investigator-assessed PD as of the data-inclusion cut-off date for the analysis, the PFS time will be censored at the date of last postbaseline adequate radiological tumor assessment, or at the date of randomization if the patient does not have any postbaseline adequate radiological assessment.
- **Overall survival (OS)** is defined as time from the date of randomization to the date of death from any cause. For each patient who is not known to have died as of the data inclusion cut-off date for a particular analysis, OS will be censored for that analysis at the date of last contact prior to the data-inclusion cut-off date (contacts considered in the determination of last contact date include AE date, lesion assessment date, visit date, and last known alive date).

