12.6.4 Response Criteria for Target Lesions

Response criteria are assessed based on the product of the longest diameter and its longest perpendicular diameter. Development of new disease or progression in any established lesions is considered progressive disease, regardless of response in other lesions – e.g., when multiple lesions show opposite responses, the progressive disease takes precedence. Response Criteria for target lesions:

- **Complete Response (CR):** Disappearance of all target lesions.
- **Partial response (PR):** $\geq 50\%$ decrease in the sum of the products of the two perpendicular diameters of all target lesions (up to 5), taking as reference the initial baseline measurements.
- **Stable Disease (SD):** Neither sufficient decrease in the sum of the products of the two perpendicular diameters of all target lesions to qualify for PR, nor sufficient increase in a single target lesion to qualify for PD.
- **Progressive Disease (PD):** 25% or more increase in the sum of the products of the perpendicular diameters of the target lesions, taking as reference the smallest sum of the products observed since the start of treatment, or the appearance of one or more new lesions.

12.6.5 Response Criteria for Non-Target Lesions:

- **Complete Response (CR):** Disappearance of all non-target lesions.
- **Incomplete Response/Stable Disease (IR/SD):** The persistence of one or more non-target lesions.
- **Progressive Disease (PD):** The appearance of one or more new lesions and/or unequivocal progression of existing non-target lesions.

12.6.6 Response criteria for tumor markers (if available):

Tumor markers will be classified simply as being at normal levels or at abnormally high levels.

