### **6.5.2. *Description of Efficacy Analyses***

Best overall response is the best response recorded from the start of treatment until disease progression, in the order of CR, PR, and SD. Best overall response will be summarized for all patients evaluable for efficacy whose disease is assessable by RECIST 1.1.

If appropriate, the following analyses will be performed.

- Objective response rate will be estimated and reported for each dose level.
- Disease control rate will be summarized and provided for each dose level.

- Progression-free survival will be estimated using a Kaplan-Meier method (Kaplan and Meier 1958) by median and 95% confidence interval (CI). Additional exploratory analyses using proportional hazards models to control for other factors may be performed.
- Overall survival will be summarized using the Kaplan-Meier method.

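### SAP 6.5.1 defines response, disease control and progression by RECIST 1.1 without exception, while the protocol scores CNS tumors (all of Part B) and neuroblastoma by other criteria

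*SAP*

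**What the plan says.** SAP Section 6.5.1 counts toward ORR those "achieving a best overall response of partial response (PR) or complete response (CR) per Response Evaluation Criteria in Solid Tumors" (it cites version 1.1), and takes everyone treated as the denominator. DCR has the same form with stable disease (SD) added. In both, a patient with no post-baseline assessment stays in the denominator as a non-responder. The PFS event is "radiographic documentation of progression (as defined by RECIST v. 1.1) based on investigator assessment", or death. The censoring rule opens with "If a patient is not known to have died or have investigator-assessed PD as of the data-inclusion cut-off date for the analysis" and does not name RECIST at that point. None of these definitions makes an exception for CNS tumors or neuroblastoma.

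SAP Section 6.5.2 gives its own best-response rule: "Best overall response is the best response recorded from the start of treatment until disease progression". That summary alone is "summarized for all patients evaluable for efficacy whose disease is assessable by RECIST 1.1". The section then states: "Objective response rate will be estimated and reported for each dose level". ORR, DCR, PFS and OS are to be done if appropriate.

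Protocol Section 5.3.2 limits Part B to CNS tumors, treated at the MTD or RP2D. For these tumors Section 12.6.4 says: "Response criteria are assessed based on the product of the longest diameter and its longest perpendicular diameter". Partial response (PR) is a fall of at least 50% in the summed products. Progressive disease (PD) is "25% or more increase in the sum of the products of the perpendicular diameters of the target lesions", or a new lesion. Section 12.6.7 adds an overall-response table that includes markers. Sections 12.4 and 12.5, with Tables 4 and 5 of 12.7.1, assess neuroblastoma by CT/MRI, MIBG, bone scan, marrow and catecholamines together. Section 11.5 names RECIST for patients with solid tumors.

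**The concern.** For a CNS patient, the rule that ends therapy is not the rule that the SAP counts. Protocol Section 10.1 removes a patient for PD as defined in Section 12, which for CNS tumors means 12.6. If that scan is not PD by RECIST, the patient stops without a RECIST progression date and is unlikely to acquire one: the table in Section 8.1 schedules no tumor evaluation off therapy, and Section 10.2 takes the patient off study 30 days after the last dose.

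The SAP does not settle the coding. Its event definition requires RECIST progression, while its censoring rule asks only whether the investigator assessed PD. Two analysts could follow the text and report different PFS for the same patient. ORR and DCR can differ as well. Antitumor activity is the only secondary aim, and Part B is small enough for one patient to show.

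**Working it through.** **Inputs.** CNS thresholds: product down at least 50% for PR, up at least 25% for PD (Protocol 12.6.4). RECIST thresholds: diameter sum down at least 30% for PR; up at least 20% and at least 5 mm for PD (Protocol 12.2.4.1). Part B: 6 evaluable, 8 enrolled, at most 15 (Protocol 11.1). The lesion sizes below are illustrative assumptions, with one target lesion and with baseline as the smallest measurement.

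**Part B size reproduced.** 6 / (1 − 0.20) = 7.5, rounded up to 8. For the expanded cohort, 12 / 0.80 = 15. Both match the protocol.

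**Proportional change.** When both diameters change by the same factor, the product ratio is the square of the diameter ratio.
- CNS PD: √1.25 − 1 = 11.8% growth in diameter.
- CNS PR: 1 − √0.5 = 29.3% shrinkage, close to RECIST's 30%.
- RECIST PD falls at the larger of 1.2d and d + 5 mm.

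| Starting diameter | CNS PD at | RECIST PD at |
|---|---|---|
| 10 mm | 11.2 mm | 15 mm |
| 20 mm | 22.4 mm | 25 mm |
| 30 mm | 33.5 mm | 36 mm |

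Between the two values the patient has PD under 12.6 and SD under RECIST.

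**Non-proportional change from 40 × 30 mm (1200 mm²).**
- To 40 × 38 = 1520 mm²: product +26.7%, longest diameter unchanged. PD by 12.6, SD by RECIST.
- To 48 × 30 = 1440 mm²: product +20%, longest diameter +20% and +8 mm. SD by 12.6, PD by RECIST.
- To 40 × 14 = 560 mm²: product −53.3%, longest diameter unchanged. PR by 12.6, SD by RECIST.

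Disagreement thus runs in both directions and can reach ORR. A new lesion is PD under both systems, so it causes none.

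**Time left to record a RECIST date.** With the last dose on day 29 and a day-42 scan, off study falls on day 29 + 30 = 59, which is 17 days after the scan.

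**Weight of one patient.** In ORR: 1/8 = 12.5 points at 8 treated Part B patients, 1/6 = 16.7 at 6, and 1/15 = 6.7 at 15. The same shift applies to DCR only if the discordant scan is the first. If SD is already on record, DCR does not change.

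**Neuroblastoma.** Table 5 allows a PR on MIBG with no measurable CT/MRI disease. Table 2, for non-measurable disease, has no PR row. That response therefore cannot be expressed under a RECIST-only definition. The number of such patients is not given.

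**Denominators.** ORR and DCR divide by treated patients; the best-response summary divides by those assessable by RECIST. The SAP does not say whether a CNS patient counts as assessable.

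**The case against.** Four objections have weight.

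- **The SAP already allows for this.** It limits the best-response summary to RECIST-assessable disease and does the other analyses only if appropriate. But the limit is not carried into ORR or DCR, PFS has none, and no criterion is named for the patients left out. The result is mismatched denominators, not a solution.
- **Protocol 11.5 names RECIST.** It does so for solid tumors, and Section 12 treats those (12.2, 12.3) separately from CNS tumors (12.6).
- **The impact is not shown.** This stands in part. The lesion sizes are illustrative. Protocol 11.6.7 lists best response and durations, to be reported descriptively; PFS and DCR are SAP additions.
- **Measurable neuroblastoma still uses CT/MRI.** This also stands. Table 4 is a composite, so the clear gap is MIBG-only disease.

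Some stronger inferences are tempting but unsupported. A reader might infer that Parts A and B will be pooled, since Part B receives the RP2D and rates are given by dose level. No passage says so, and Protocol 11.6.4 speaks of dose cohorts. A reader might see a conflict between central review in 12.4.3 and investigator-assessed PFS. The first concerns MIBG response and the second radiographic progression, so naming the assessor is a clarification. A reader might also expect Table 3 of Protocol 12.7.1 to lower DCR. It does not under the SAP as written, because 6.5.2 has its own best-response rule.

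**Conclusion.** The mismatch is real and is wrong as written. SAP 6.5.1 would score Part B by criteria that the protocol does not use for those patients or for ending their therapy. The RECIST-assessable limit in 6.5.2 does not cure it. For proportional growth the gap is 11.8% against 20% in diameter, wider for lesions under 25 mm because of the 5 mm minimum. One reclassified patient is worth 12.5 points at 8 treated.

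The reach is limited. Only descriptive, conditional secondary results are affected; MTD, RP2D, safety and PK are not. The documents do not support any statement that results will be biased in a given direction or by a given amount, because the number of discordant patients is unknown and may be zero.

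Two secondary inconsistencies lie in the protocol. In 12.6.4 the SD line refers to growth in one target lesion, while the PD line refers to the sum. In 12.7.1, Table 3 codes SD, PR or CR followed by progression as PD, while Table 1 attaches PD to patients with no earlier SD or response. Section 12.7.1 also requires confirmation, which the SAP rule does not mention.

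**What to change.** **SAP 6.5.1.** Derive response and progression by the disease-specific criteria of Protocol Section 12: 12.2 and 12.3 for solid tumors, 12.4 and 12.5 with Tables 4 and 5 for neuroblastoma, 12.6 for CNS tumors. Use the same reference in the PFS event and censoring rules, so that one definition of PD governs both.

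**Reporting.** Present Part B separately. State one denominator for ORR, DCR and best response.

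**Secondary, in the protocol.** Reconcile the SD and PD wording in 12.6.4; because PD ends therapy, this note takes no position on which wording should stand. Reconcile Table 3 with Table 1, with the best-response rule and with the confirmation requirement in 12.7.1, and point SAP 6.5.2 to the result. This should not bring in a rule for unconfirmed responses that the documents do not contain.

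**Cost.** SAP wording and a short protocol clarification. No added patients or scans are needed, since the scheduled evaluations already call for the Section 12 measurements.

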- ¹ Women of childbearing potential require a negative pregnancy test prior to starting treatment and before starting each subsequent cycle; sexually active patients must agree to use a highly effective method of contraception during protocol therapy and for at least 3 months after the last dose of ramucirumab. Abstinence is an acceptable method of birth control.
- ² Blood pressure will be measured with an appropriate sized cuff at rest. Blood pressure measurement will be repeated within the same day if the blood pressure (BP) is elevated (> the 95th percentile for age, height, and gender). Please note that 3 serial blood pressures should be obtained and averaged to determine baseline BP (See [Section 6.4](#)). If both BP measurements are >95th percentile for age, height, and gender, follow the guidelines in [Section 6.4](#). Patients with elevated BP at any time should have BP measurements performed at least twice weekly until BP is within the 95th percentile for age, height, and gender (See [Appendix VIII](#)).
- ³ If patients have Grade 4 neutropenia then CBCs should be checked at least every other day until recovery to Grade 3 or until meeting the criteria for dose limiting toxicity.
- ⁴ If patients develop Grade 4 neutropenia then CBCs should be checked every 3 to 4 days until recovery to Grade 3.
- ⁵ See [Appendix IX](#) for UPC rationale and calculation and [Section 6.5](#) for dose modifications if UPC > 1. If patient is being followed for prior proteinuria and UPC is obtained at the scheduled time points, urinalysis is not also required. If patient has proteinuria (urine protein/creatinine (P/C) ratio >1), a second measurement should be obtained within 72 hours.
- ⁶ Tumor Disease Evaluation should be obtained on the next consecutive cycle after initial documentation of either a PR or CR. Subsequent scans may restart 2 cycles after the confirmatory scan. Please note that for solid tumor patients, if the institutional investigator determines that the patient has progressed based on clinical or laboratory evidence, he/she may opt not to confirm this finding radiographically. For patients with CNS disease (Part B), ECHO gradient MRI sequences per institutional standards are required to evaluate for hemorrhage (See [Appendix X](#)).

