10.0 CRITERIA FOR REMOVAL FROM PROTOCOL THERAPY AND OFF STUDY CRITERIA

10.1 Criteria for Removal from Protocol Therapy

- a) Clinical (including physical examination or serum tumor markers) or radiographic evidence of progressive disease (See [Section 12.0](#)).
- b) Adverse Events requiring removal from protocol therapy (See [Section 6.0](#)).
- c) Refusal of protocol therapy by patient/parent/guardian
- d) Non-compliance that in the opinion of the investigator does not allow for ongoing participation.
- e) Completion of 8 cycles of therapy.
- f) Physician determines it is not in the patient's best interest.
- g) Repeated eligibility laboratory studies (CBC with differential, bilirubin, ALT (SGPT) or serum creatinine) are outside the parameters required for eligibility prior to the start of ramucirumab (See [Section 8.1](#)).
- h) Study is terminated by Sponsor.
- i) Pregnancy

Patients who are removed from protocol therapy during cycle 1 should continue to have the required observations in [Section 8.1](#) until the originally planned end of the cycle or until all adverse events have resolved per [Section 13.4.4](#), whichever happens LATER. The only exception is with documentation of the patient's withdrawal of consent. Patients who are removed from protocol therapy in subsequent cycles should have the necessary observations to ensure adequate clinical care.

Patients who are off protocol therapy are to be followed until they meet the criteria for Off Study (see below). Ongoing adverse events, or adverse events that emerge after the patient is removed from protocol therapy, but within 30 days of the last dose of investigational agent, must be followed and reported via RAVE and CTEP-AERS (if applicable). Follow-up data will be required unless consent is withdrawn.

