10.2 Off Study Criteria

- a) Thirty days after the last dose of the investigational agent.
- b) Death
- c) Lost to follow-up
- d) Withdrawal of consent for any required observations or data submission.
- e) Enrollment onto another COG therapeutic (anti-cancer) study
- f) Patient did not receive protocol treatment after study enrollment

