12.3.5 Progressive Disease

The appearance of one or more new lesions or evidence of laboratory, clinical, or radiographic progression.

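### The SAP's PFS counts only radiographic progression or death, but the protocol allows progression to be declared without a scan; the resulting informative censoring biases Kaplan-Meier PFS upward

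*SAP*

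**What the plan says.** **SAP 6.5.1, event.** PFS runs "until the date of radiographic documentation of progression (as defined by RECIST v. 1.1) based on investigator assessment or the date of death". Clinical or laboratory progression is not listed as an event.

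**SAP 6.5.1, censoring.** The trigger is worded differently: "If a patient is not known to have died or have investigator-assessed PD as of the data-inclusion cut-off date". For such a patient "the PFS time will be censored at the date of last postbaseline adequate radiological tumor assessment". Someone with no usable scan after baseline is instead censored on the randomization date. The trial is not randomized, so I read that date simply as time zero.

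**SAP 6.5.2.** PFS is summarized by a Kaplan-Meier median with a 95% CI, if appropriate. There is no rule and no sensitivity analysis for progression without a scan.

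**Protocol 8.1, footnote 6.** If the investigator of a solid-tumor patient finds that the patient has "progressed based on clinical or laboratory evidence, he/she may opt not to confirm this finding radiographically".

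**Protocol 10.1(a).** Grounds for removal from therapy include "Clinical (including physical examination or serum tumor markers) or radiographic evidence of progressive disease".

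**Protocol 12.3.5.** In patients with evaluable but no measurable disease, who are eligible under 4.1.3, PD is "The appearance of one or more new lesions or evidence of laboratory, clinical, or radiographic progression".

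**Protocol 8.1 table and 10.2.** Tumor evaluations fall at the end of cycles 1 and 2 and then every other cycle (about days 42, 84, 168, 252 and 336). None is marked at the off-therapy visit. A patient is off study "Thirty days after the last dose of the investigational agent".

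**The concern.** The two documents use different definitions of progression. A child whose disease progresses on examination or markers, who stops therapy for that reason and is not scanned, has progressed under the protocol but has no PFS event under the SAP unless death is captured.

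Censoring at the last scan assumes that the patient's later prospects match those of patients still followed. Here progression itself causes the censoring, so that assumption fails. Patients who progress clinically before the first scan at day 42 are affected most: censored at time zero, they never enter the risk set. What is at stake is the credibility of the PFS estimate reported under the secondary aim of antitumor activity.

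**Working it through.** The documents give no PFS figure, event count or power, so there is nothing to reproduce. The check concerns the direction of the bias and its possible size.

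**Inputs from the documents:** the event and censoring rules and the scan days above. **Assumed:** the true PFS, and the share q of progressions declared without a scan.

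**Step 1: closed form at the first scan.** Let p be the true probability of progression by week 6. A fraction pq is censored at time zero, leaving 1 − pq at risk at the first scan, where p(1 − q) have events. With no captured deaths the SAP rule estimates

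PFS(6 weeks) = 1 − p(1 − q)/(1 − pq) = (1 − p)/(1 − pq),

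which exceeds the true 1 − p whenever q > 0. With p = 0.5:

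| q | SAP rule | True |
|---|---|---|
| 10% | 0.5/0.95 = 52.6% | 50% |
| 20% | 0.5/0.90 = 55.6% | 50% |
| 30% | 0.5/0.85 = 58.8% | 50% |
| 40% | 0.5/0.80 = 62.5% | 50% |

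**Step 2: a hypothetical cohort of 12.** Three have clinical PD in cycle 1 without a scan, four have radiographic PD at day 42, and five are progression-free. Counting every progression gives 5/12 = 42%. The SAP rule drops the three and gives 1 − 4/9 = 56%.

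**Step 3: later scans.** This was simulated with 20,000 patients per setting, exponential progression times and the protocol scan days. For a true median of 60 days and no captured deaths, day-84 PFS was:

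| q | SAP rule | Clinical PD counted |
|---|---|---|
| 10% | 0.41 | 0.37 |
| 20% | 0.44 | 0.37 |
| 30% | 0.48 | 0.38 |
| 40% | 0.53 | 0.38 |

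If 25% of unscanned progressors die within 30 days and so become events, the q = 30% gap narrows to 0.46 versus 0.38. Across true medians of 42, 60 and 90 days, with and without those deaths, the excess at days 84 and 168 was about 1 to 3 percentage points at q = 10% and 5 to 15 points at q = 40%.

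**Step 4: the median.** Radiographic events can fall only on scan days, so the reported median jumps between them. With a true median of 6 weeks, the curve sits at 0.50 on the first scan day even when q = 0, and a simulation with q = 0 (0.501 at week 6) already reported 12 weeks. With a true median of 5 weeks, 1 − p = 2^(−6/5) = 0.435. The step 1 formula then gives 0.461 at q = 10% and 0.491 at q = 20%, so the median stays at 6 weeks. At q = 30% it gives 0.524, and the median moves to 12 weeks. At true medians of 7 and 9 weeks with q of 10 to 20%, it is 12 weeks under both rules.

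**Step 5: event against censoring wording.** An unscanned clinical progressor fails the event definition, which requires radiographic documentation. Read literally, the same patient also fails the censoring trigger if a site-declared PD counts as investigator-assessed PD. The text then assigns no PFS time. Reading the trigger in line with the event definition gives the censoring analyzed above. On neither reading is the clinical progression date an event.

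**The case against.** **Radiographic-only PFS is a legitimate choice.** In an open-label trial, objective progression limits investigator discretion, and clinical PD is less standardized. This stands for measurable disease and is why the main definition there need not be replaced. It does not cover evaluable-only disease, where the protocol itself makes clinical or laboratory progression PD.

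**The SAP does not plainly say that these patients are censored.** This also stands: the trigger names investigator-assessed PD. The sound claim is that the wording is inconsistent and that the reading in line with the event definition censors them.

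**Some cases are recovered.** Protocol 10.1 keeps patients removed in cycle 1 on the required observations at least to the planned end of that cycle, and a tumor evaluation is scheduled then. Protocol 12.7.1 asks for best efforts to document objective progression after symptomatic deterioration. Deaths within follow-up count as events. These reduce q or its effect: if half of a 20% share were scanned after all, step 1 would give 52.6% instead of 55.6%. They do not close the gap, because footnote 6 still waives the confirming scan and follow-up is short. A reader might infer that deaths will hardly ever recover these cases, but the documents give no figure for that.

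**PFS is peripheral here.** It is not named in the protocol's aims or in its Section 11 methods, the protocol calls its response analyses descriptive (11.5), and the SAP runs PFS only if appropriate. This limits the importance of the point, not its correctness.

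**Conclusion.** The concern holds as a definitional mismatch that biases Kaplan-Meier PFS upward at the scan dates. Under the assumptions of a true 6-week PFS of 50%, 10 to 40% of progressions unscanned and no captured deaths, 6-week PFS reads about 53 to 63%. The real share is not in the documents, so the actual bias cannot be calculated; captured deaths and cycle 1 observations would reduce it. Footnote 6 names solid-tumor patients, so Part B is less exposed.

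Two stronger readings are not supported. A reader might infer that the reported median would double from 6 to 12 weeks, but at that setting the scan grid alone yields 12 weeks, and at several others the median does not move. A reader might also infer that disease control in general is overstated. SAP 6.5.1 keeps patients with no post-baseline assessment in the ORR and DCR denominators as non-responders, so those rates do not share the bias. MTD and RP2D rest on DLTs and trough concentrations and are unaffected.

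This merits correction before analysis, at moderate priority.

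**What to change.** In SAP 6.5.1:

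1. Make the event and censoring wording agree, and state how PD without a scan is handled.
2. For evaluable-only disease, count PD as defined in Protocol 12.3.5 as a PFS event.
3. For measurable disease, keep radiographic PFS as the main analysis. Add a sensitivity analysis that counts investigator-declared clinical or laboratory PD ending therapy under Protocol 10.1(a) as an event on its date, or on the off-therapy date if the declaration is not dated.
4. Report the number of patients censored at baseline and the number with clinical-only PD.

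The cost is SAP wording and one further Kaplan-Meier estimate, with no new visits or scans. The case report form is not among the documents, and SAP 6.2 lists discontinuation reasons only where known. The sponsor should therefore confirm that clinical and radiographic PD can be told apart in the data; the off-therapy date covers a missing declaration date. The downside is that clinical PD is less standardized and the added estimate will be somewhat less favourable.
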